- Estimated minimum and maximum number of women for follow up of pertussis vaccine 1,527–20,358

Sample size and power

As this is an observational study we plan to describe the confidence intervals for the proportions of AEs. With a sample of 300 vaccinated participants, if event occurs in 10% of the group the 95% CI would be 7–14%; if 5%, 2.8–8.1%; if 1%, 0.2–2.9%. Additional power will be achieved by combining the data from the Canterbury study (Study Three), which aims to include 300 women vaccinated with Tdap.

Statistical Analyses

The pregnancy safety data will be descriptive in nature, including percentages and 95% confidence intervals. The rates of AEs and SAEs following pertussis vaccine will be discussed in context with the rates previously described for pertussis. The expected background rates of MAEs and SAEs for Tdap given during pregnancy are unknown, but as a guide the rates of MAEs for pregnant women receiving influenza vaccine previously reported ranged from 1.1 to 3.8% while the rate of SAEs ranged from 0.4 to 1.5%.

Women who have complicated pregnancies will be excluded from the final analyses and described separately.

The temporal relationship between onset of events and vaccination will be presented including distribution where appropriate.

Serious adverse events will be reported as detailed clinical cases. Other events will be groups according to Brighton Collaboration Definitions.

Study Three (N=~300)

From the protocol for Canterbury DHB (Appendix 8): Principal Investigator, [name].

As this study is an observational study, the pregnancy outcomes and safety data will be descriptive in nature. The rates of AEs and SAEs will be compared to published background rates for the general population. The expected rates of MAEs and SAEs for Tdap given during pregnancy is unknown, but as a guide the rates of MAEs for pregnant women receiving influenza vaccine in this paper ranged from 1.1 to 3.8% while the rate of SAEs ranged from 0.4 to 1.5%. Where the known background incidence of 0.01 for a particular adverse event, a sample size of 300 achieves 80% power to detect an additional incidence rate of 0.0175 when the significance level is 0.05.

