It is anticipated that the difference in AEs between subgroups in the trial will be small. As this is an observational study we therefore plan to describe the confidence intervals for the proportions of AEs within each group. A sample size of 300 produces a two-sided 95% confidence interval with a width equal to 0.081 when the sample proportion is 0.150.

Women who have multiple pregnancies and/or complicated pregnancies will be excluded from the final analyses and described separately.

Total expected participants

	Study population	Sample size	
--	------------------	-------------	--

Study One	325,000		Total pertussis-vaccinated maternal population
Study Two	1,527–20,358	300	~300 pertussis vaccinees
Study Three	6,000	300	300 pertussis vaccinees

Vaccines

Pertussis vaccine

The pertussis vaccine funded for pregnant women is Boostrix[®]. There are other licensed vaccines but no other pertussis vaccines currently funded for pregnant women in NZ.

Specific vaccine supply requirement

N/A. This is an observational study. There are no vaccine requirements for this study.

Adverse experience reporting

Adverse Event data are being accessed/collected during this project in Study Two and Three.

The Investigator will report SAEs (either initial or follow-up reports) to:

The NZ Centre for Adverse Reaction Monitoring (CARM) at the University of Otago according to local requirements. (See Appendix 9, contract Exhibit D, CARM Reporting Form)

The Ethics Committee according to requirements

The Marketing Authorisation Holder within 24 hours according to contracted safety reporting requirements defined in the study contract. Case reporting will include the relevant variables in the GSK “with intensity GCSP reporting form”. (See Appendix 10)

Administration during pregnancy is relevant in the age group, so pregnancy reporting is expected to be relevant. All participants will be pregnant.

There will be no causality assessments conducted during this study as this is observational and there is no intervention.

Any adverse events that are reported to the NZ Centre for Adverse Reaction Monitoring (CARM) undergo causality assessment. This data is provided to the WHO and the MoH.

CARM is the official regulatory body in charge of receiving all adverse event reports in NZ. CARM collaborates with and pools anonymised data, together with other national monitoring centres, into the database of the World Health Organization's International Drug Monitoring Programme.

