It is anticipated that the difference in AEs between subgroups in the trial will be small. As this is an observational study we therefore plan to describe the confidence intervals for the proportions of AEs within each group. A sample size of 300 produces a two-sided 95% confidence interval with a width equal to 0.081 when the sample proportion is 0.150.

Women who have multiple pregnancies and/or complicated pregnancies will be excluded from the final analyses and described separately.

Related research

In studies of pertussis booster vaccines administered alone or together with influenza vaccine in people 19–64 years of age,¹⁸ adverse reactions were generally mild-to-moderate in intensity. The overall reactogenicity profile of the Tdap and influenza vaccines, in terms of incidence of solicited local symptoms (injection site pain, redness and swelling), as well as the incidence of solicited general symptoms (fatigue, fever, gastrointestinal symptoms, headache, joint pain, muscle aches, and shivering) was generally similar between the co-administration and sequential vaccine groups (Figure).⁸ The most frequently reported local and general solicited symptoms in both vaccine groups were injection site pain and muscle aches, respectively.⁸ Unsolicited adverse events were reported by similar percentages of subjects in both groups (about 20%).⁸

The local symptom report rate was 48.9% after *Fluarix* and 61.6% after *Boostrix*. The rate of unsolicited AE reporting was 17.4% (14.7-20.3) after *Fluarix*, 14.6% (12.1 to 17.3) after *Boostrix*, and 21.5% (18.6-24.6%) after co-administration with both vaccines. The report rate of unsolicited AE causally related to vaccination was 4.3% (2.9 to 6.0) after *Fluarix*, 2.4% after *Boostrix* (1.4-3.8) and 7.0% (5.2-9.0) after co-administration.

The *Boostrix* Data Sheet notes that when Tdap and seasonal influenza vaccine are coadministered in adults, lower levels of antibodies to FHA and pertactin are induced compared to Tdap alone.¹⁹ It is not known if the efficacy of *Boostrix* is affected.⁹

¹⁸ Weston WM et al. Safety and immunogenicity of a tetanus toxoid, reduced diphtheria toxoid, and acellular pertussis vaccine when co-administered with influenza vaccine in adults. *Hum Vaccin*. 2009;5(12):858-66.

¹⁹ GlaxoSmithKline New Zealand. *Boostrix* Data Sheet. GSKNZ; 2011. Available at www.medsafe.govt.nz

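### Study Three's stated 80% power rests on an unstated one-sided large-sample approximation; tests that hold the 5% level give 72%, or 58% if judged by an equal-tailed exact 95% interval

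*Protocol*

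**What the plan says.** The Study Three paragraphs of the protocol's section on statistical analysis and sample size describe the analysis as descriptive. For context they add: "The rates of AEs and SAEs will be compared to published background rates for the general population". The power statement follows. It starts from "Where the known background incidence of 0.01 for a particular adverse event" and concludes that "a sample size of 300 achieves 80% power to detect an additional incidence rate of 0.0175 when the significance level is 0.05". Appendix 8 (Canterbury Protocol, Statistical Analysis) repeats the same sentence.

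Neither place says which test is meant or whether 0.05 is one-sided or two-sided. The next paragraph turns to precision: "A sample size of 300 produces a two-sided 95% confidence interval with a width equal to 0.081 when the sample proportion is 0.150". There, two-sided describes the interval, not the power calculation.

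In the same section, Study Two gives 95% intervals for 300 women: 7–14% at an observed 10%, 2.8–8.1% at 5%, and 0.2–2.9% at 1%.

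**The concern.** The comparison is between one group of 300 and a rate treated as known, so it is a one-sample binomial problem. At 1% only 3 events are expected, and at 2.75% only 8.25. Normal-theory power formulas are unreliable with counts this small, because the achievable significance levels move in large steps and the null distribution is skewed.

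This is Study Three's only power statement. The 1% background lies inside the 0.4–1.5% range that the protocol offers as a guide for serious adverse events, so the sentence bears on serious events in vaccinated pregnant women. A reader who takes it at face value would think that a rise to nearly three times background would be missed one time in five. If the true chance of missing it is higher, an unremarkable result would seem more reassuring than it is.

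**Working it through.** **Inputs, all from the Study Three text.** n = 300; background p0 = 0.01; additional incidence 0.0175, so p1 = 0.0275; significance level 0.05. Expected events are 300 × 0.01 = 3 under the background and 300 × 0.0275 = 8.25 under the alternative.

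**1. Reproducing the 80%.** The one-sample normal approximation is

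power = Φ[(p1 − p0 − z·√(p0(1−p0)/n)) / √(p1(1−p1)/n)].

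The standard errors are √(0.01 × 0.99/300) = 0.005745 and √(0.0275 × 0.9725/300) = 0.009442.

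- One-sided, z = 1.645: (0.0175 − 1.645 × 0.005745)/0.009442 = 0.853, so power = 80.3%. This matches.
- Two-sided, z = 1.960: (0.0175 − 1.960 × 0.005745)/0.009442 = 0.661, so power = 74.6%. This does not.

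Other forms were tried. A Poisson-variance version of the one-sided formula gives 79.8%. With continuity correction the results are 75.1% (one-sided) and 68.6% (two-sided); with the arcsine transformation 74.4% and 63.4%; with a two-sample comparison of 300 per group 47.4% and 35.2%. Of the forms tried, only one-sided large-sample formulas give 80%.

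**2. What that test does on whole counts.** The one-sided z-test rejects when the count exceeds 300 × (0.01 + 1.645 × 0.005745) = 5.83, that is, at 6 or more events. Binomial tails for n = 300:

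| Reject at | P(reject) at 1% | P(reject) at 2.75% |
|---|---|---|
| 6 or more | 8.3% | 83.4% |
| 7 or more | 3.3% | 72.0% |
| 8 or more | 1.1% | 58.4% |

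The rule behind the 80% therefore has a type I error of 8.3%, not 5%. The smallest cut-off that holds 5% in the upper tail is 7 events, with power 72.0%.

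**3. The two-sided case.** The answer depends on which two-sided method is used.

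- *Exact test ordered by point probability.* At 7 events p = 0.033. In the lower tail the only candidate is zero events, whose probability at 1% (0.049) exceeds that of 7 events (0.021), so it adds nothing. The test rejects at 7, and power is 72.0%.
- *95% Wilson interval.* At 7/300 the lower limit is 1.13%, which excludes 1%. Power is again 72.0%.
- *95% equal-tailed exact (Clopper-Pearson) interval.* At 7/300 it is 0.94–4.75%, which includes 1%; at 8/300 it is 1.16–5.19%, which excludes it. The cut-off is 8, and the probability of excluding 1% from below is 58.4%.

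The Clopper-Pearson method reproduces Study Two's printed limits: 3/300 gives 0.21–2.89% and 15/300 gives 2.83–8.11%. The Wilson method gives 0.34–2.90% and 3.05–8.08%, so its lower limits do not match.

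**4. The rise that does have 80% power with 300 women.** Solving P(X ≥ 7) = 0.80 gives a true rate of 3.01%, an excess of 0.020. Solving P(X ≥ 8) = 0.80 gives 3.39%, an excess of 0.024. The printed excess is 0.0175.

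**The case against.** The strongest reply is that nothing has been miscalculated. A recognised formula gives 80.3%, and a one-sided reading is natural for a sentence about detecting an excess over background. The choice of test is often left to a statistical analysis plan. That disposes of any charge of an arithmetic slip. It does not rescue the figure, because even on the one-sided reading a test that holds 5% has 72% power, and the protocol itself prints the number, twice.

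A reader might also infer that 58% is the exact two-sided power. The documents do not support that. Two common two-sided methods reject at 7 events and give 72%. The 58% belongs to the equal-tailed Clopper-Pearson interval, which is inferred from Study Two's figures and not stated for Study Three.

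A further tempting step is to attack the interval width of 0.081, since intervals are promised for each group and Tdap recipients divide into those with and without influenza vaccine. That does not stand. The width is correct and labelled as being for 300 women, the primary objectives cover all Tdap recipients, and the documents give no expected group sizes from which to work out another width.

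Finally, the consequence is limited. The study is descriptive and plans intervals, with no formal test for this comparison. Appendix 8 arrives at 300 from expected uptake and the funding period, not from power. Study Two's printed interval of 0.2–2.9% at an observed 1% already shows that 2.75% would not be excluded. One-month maternal outcomes may be pooled with Study Two; with about 600 women, exact power at 2.75% is 94% one-sided (11 or more events) or 90% equal-tailed (12 or more). All of this stands as a bound on the harm. Pooling does not cover infant outcomes, and the printed sentence is about 300 women.

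**Conclusion.** The concern holds in this form: the 80% comes from an undisclosed one-sided large-sample approximation, used where only 3 events are expected and where its real type I error is 8.3%. With the level held at 5%, power for 1% rising to 2.75% is 72%, by the one-sided exact test and also by the two-sided exact test ordered by point probability. It is 58% if the criterion is that an equal-tailed exact 95% interval excludes 1%. The chance of missing such a rise is thus 28% to 42%, against the 20% that the text implies.

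These figures assume that the background rate is fixed and known, as the protocol does, and that all 300 women are analysed. The text excludes multiple and complicated pregnancies from the final analyses. That would lower the number analysed, but the documents give no share for Study Three, so no allowance is made. No design feature or planned decision changes; what is wrong is how the study's capability is described.

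**What to change.** In the Study Three power sentence, and in the same sentence of Appendix 8, name the test and its sidedness and restate the figures. Suggested content: with 300 women and a background of 1%, a one-sided exact binomial test at the 5% level has about 72% power for a rise to 2.75% and 80% power for a rise to about 3.0%; a two-sided 95% equal-tailed exact interval would exclude 1% with probability about 58% at 2.75% and 80% at about 3.4%. Keep the words equal-tailed, since the last two figures do not apply to every exact two-sided method. Leave the interval-width sentence as it is.

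The cost is an edit to one sentence in two places. No extra participants, data or analyses are needed.

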¹⁵ New Zealand Ministry of Health. Current advice on the public health management of pertussis. Wellington: MoH; 5 April 2012. Available at http://www.nzdoctor.co.nz/media/1682109/pertussis_letter_moh_5_apr_2012.pdf

¹⁶ New Zealand Ministry of Health. Chapter 15: Influenza. In Immunisation Handbook 2011. Wellington: MoH; 2011. Available at http://www.google.co.nz/url?sa=t&rct=j&q=ministry%20health%20influenza%20vaccine%20pregnant%20women%20funded%20&source=web&cd=7&ved=0CGYQFjAG&url=http%3A%2F%2Fwww.health.govt.nz%2Fsystem%2Ffiles%2Fdocuments%2Fpublications%2F15influenza.pdf&ei=8SiWT8iDH4_m8Q0gnNGMCg&usg=AFQjCNFUuAYDXQKxJFmtqXKd4PBfzm1i2A

¹⁷ Canterbury District Health Board. Media release from Canterbury DHB: Free whooping cough vaccine extended to pregnant women. Christchurch: CDHB; April 19, 2012.

- To compare adverse event rates in women who were vaccinated with Tdap, seasonal influenza vaccine or both
- To describe outcomes of babies whose mothers were vaccinated with the seasonal influenza during pregnancy (including birth history, weight and head circumference and any congenital abnormalities)
- To describe outcomes of babies whose mothers were vaccinated with the seasonal influenza and also received Tdap during weeks 30-36 of pregnancy (including birth history, weight and head circumference and any congenital abnormalities)
- To Evaluate infants of mothers vaccinated with Tdap, seasonal influenza vaccine or both during pregnancy who have symptoms consistent with pertussis or who have had significant contact with a proven case

Study design

This is a prospective observational cohort study. It will describe any adverse events in pregnant mothers who received either Tdap or influenza vaccine, or both. Outcomes for their infants will also be measured and described. Infants of mothers vaccinated with Tdap, seasonal influenza vaccine or both during pregnancy who have symptoms consistent with pertussis or who have had significant contact with a proven case will also be evaluated. The funded brands of Tdap are Boostrix and Adacel, and the funded brands of influenza are Fluarix and Fluvax).

Study population

Women vaccinated during pregnancy with Tdap will be identified through the GP record of claims for the administration of the vaccine as soon as possible after administration of the vaccine. Women from the same GP practices who have had trivalent inactivated influenza vaccine during pregnancy will also be identified and enrolled..

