Funding for Tdap is being offered postpartum as well as during pregnancy, so women may choose to wait until their babies are born to take up the offer. Funding for the vaccine has approved for an initial period of 6 months with a view to extending for another 6 months if the pertussis outbreak continues. Previous outbreaks in New Zealand have lasted in the order of 18 months so it is likely that funding will continue beyond 6 months. We would therefore aim to enroll 300 women who have received Tdap vaccine.

Study groups

Group 1) received Tdap vaccine while pregnant (30 to 36 weeks gestation).

Group 2) received trivalent inactivated influenza vaccine while pregnant

Group 3) received both Tdap and trivalent inactivated influenza vaccine, separately or coadministered during pregnancy

Inclusion criteria

Women

- Pregnant women 18-40 years of age who have received either the Tdap vaccine between 30-36 weeks gestation, or received the influenza vaccine at any stage during pregnancy or both
- Compliant with routine antenatal care, including at least 1 ultrasound early in pregnancy
- Information regarding which brand vaccine of was given (if the brand is not available, batch number and expiry is sufficient as this will help to ascertain which brand was given)

Infants:

- Infants of the women who were vaccinated with the Tdap vaccine, seasonal influenza vaccine or both during pregnancy

Exclusion criteria

- Pregnant women who have received the Tdap vaccine prior to 30 weeks gestation or after 36 weeks gestation
- If a woman has already had her baby prior to being contacted by the the study team, she will not be enrolled in the study

Statistical Analysis

As this study is an observational study, the pregnancy outcomes and safety data will be descriptive in nature. The rates of AEs and SAEs will be compared to published background rates for the general population (summarised in Tavares et al¹⁰). The expected rates of MAEs and SAEs for Tdap given during pregnancy is unknown, but as a guide the rates of MAEs for pregnant women receiving influenza vaccine in this paper ranged from 1.1 to 3.8% while the rate of SAEs ranged from 0.4 to 1.5%. Where the known background incidence of 0.01 for a particular adverse event, a sample size of 300 achieves 80% power to detect an additional incidence rate of 0.0175 when the significance level is 0.05.

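### Study Three sets a secondary objective to compare AE rates between vaccine groups but plans only within-group intervals, and the quoted width of 0.081 holds for all 300 Tdap women together, not for each group

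*Protocol*

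**What the plan says.** Appendix 8, Secondary Objectives, includes: "To compare adverse event rates in women who were vaccinated with Tdap, seasonal influenza vaccine or both". Appendix 8, Study groups, defines three groups. Group 1 received Tdap. The other two are "Group 2) received trivalent inactivated influenza vaccine while pregnant" and "Group 3) received both Tdap and trivalent inactivated influenza vaccine, separately or coadministered during pregnancy".

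The size target in Appendix 8, Expected sample size, is for Tdap recipients as a whole: "We would therefore aim to enroll 300 women who have received Tdap vaccine". The main protocol repeats it as 300 pertussis vaccinees in its table of total expected participants. No size is given for any of the three groups, and none at all for influenza vaccine alone.

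The statistical text for Study Three appears in the main protocol and again in Appendix 8. It calls the outcome and safety data descriptive and names one comparison, against published background rates. On the groups it says: "It is anticipated that the difference in AEs between subgroups in the trial will be small". From that it concludes: "As this is an observational study we therefore plan to describe the confidence intervals for the proportions of AEs within each group". The next sentence gives a 95% interval width of 0.081 for a sample of 300 and a proportion of 0.150. Multiple and complicated pregnancies are then removed from the final analysis.

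**The concern.** A comparison of rates needs an estimate of how far they differ, with its uncertainty. A row of one-sample intervals does not supply one. Expecting a small difference is no reason to leave it unestimated, because a small difference can be claimed only from an interval for the difference. Placed side by side, such intervals invite a reader to check whether they overlap, which is a much stricter criterion than a direct comparison at the 5% level.

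The precision sentence has a related fault. It follows directly on the plan for intervals within each group, so it reads as the precision of each group, while its sample size is the whole Tdap target. At stake is a secondary safety objective that the stated analysis does not answer, with precision that looks better than the groups will have.

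**Working it through.** **1. The plan's own figure.** Inputs: n=300 and p=0.150, from the Study Three statistical text. Width = 2 × 1.96 × √(p(1−p)/n) = 3.92 × √(0.1275/300) = 3.92 × 0.02062 = 0.0808. The stated 0.081 is reproduced.

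**2. Which women the 300 are.** The 300 are all Tdap recipients. For a comparison of Tdap, influenza vaccine or both, Group 1 has to mean Tdap without influenza vaccine, so Groups 1 and 3 share the 300. The split is not stated. The same formula at p=0.15 gives:

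| Group size | Width |
|---|---|
| 300 | 0.081 |
| 250 | 0.089 |
| 200 | 0.099 |
| 150 | 0.114 |
| 100 | 0.140 |

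An even split widens the interval by a factor of √2, about 41%. The later exclusion of multiple and complicated pregnancies widens it further, by an amount that cannot be computed from the documents.

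**3. What separate intervals show about a difference.** Illustrative rates come from Appendix 8, Related research: unsolicited AEs 14.6% after Boostrix and "21.5% (18.6-24.6%) after co-administration with both vaccines". Assumed split: 150/150.

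- Standard errors: √(0.146 × 0.854/150) = 0.0288 and √(0.215 × 0.785/150) = 0.0335. For the difference: √(0.0288² + 0.0335²) = 0.0442.
- Direct two-sided 5% test, pooled p=0.1805: null SE = √(2 × 0.1805 × 0.8195/150) = 0.0444. Power = Φ[(0.069 − 1.96 × 0.0444)/0.0442] = Φ(−0.41) = 34%.
- Non-overlap of two separate 95% intervals: Φ[(0.069 − 1.96 × (0.0288 + 0.0335))/0.0442] = Φ(−1.20) = 11%. Full binomial enumeration with Clopper-Pearson intervals gives 9%.
- Level of the non-overlap criterion with equal standard errors: 2 × [1 − Φ(1.96√2)] = 0.6%, against 5% for the direct test.

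**4. What a direct estimate would show.** If those rates were observed at 150/150, the interval for the difference would be 6.9 ± 1.96 × 4.42 = 6.9 ± 8.7 points, or about −1.8 to 15.6. A reader sees at once that neither no difference nor a large one is excluded.

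**5. How far size alone limits the answer.** Over splits from 50/250 to 250/50, direct power for 14.6% against 21.5% runs from 17% to 34%. It is 59% at 300/300, and 80% power needs 487 per group. From a base of 15%, the smallest difference detectable with 80% power at 150/150 is 13.3 points.

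**The case against.** Several points on the other side stand.

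- No passage says the group intervals will be compared by overlap, or that overlap will be reported as agreement. A reader might infer such a rule from the stated expectation of small differences, but the text does not support attributing it to the plan. Step 3 therefore shows a risk of misreading, not a planned test. Group proportions with their denominators would also let a reader compute the difference.
- A reader might infer that the protocol's cited data refute the expectation of small differences. They do not settle it. The same section reports unsolicited AEs as similar, about 20%, in the co-administration and sequential groups. Group 3 includes vaccines given separately, and the cited subjects are adults aged 19 to 64. The wider contrast cited there, 2.4% against 7.0%, concerns events judged causally related to vaccination. The protocol states that Study Three makes no causality assessment, so that contrast matches no planned outcome.
- Low power is mainly a matter of size. A direct test at 150/150 would still miss 14.6% against 21.5% about 66% of the time.
- The figure 0.081 is not a miscalculation. It is the right precision for the primary objective, which concerns all Tdap women.
- The comparison is one of several secondary objectives and appears only in Appendix 8. The Study Three objectives in the main protocol are descriptive and concern Tdap only.

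The choice of contrast is often left to an SAP. Here, however, the protocol itself selects within-group intervals and gives its reason for doing so, so the mismatch with the objective lies in its own text.

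**Conclusion.** The point holds in limited form. A stated secondary objective to compare groups is met by an analysis that estimates no difference, and a precision figure that is correct for all 300 Tdap women is placed where it reads as applying to each group.

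For precision, per-group widths at p=0.15 are about 0.089 to 0.140 for groups of 250 down to 100, instead of 0.081. For the comparison, at 150/150 a 6.9-point difference would be flagged about 9 to 11% of the time if intervals were read by overlap, against 34% directly. These figures rest on an assumed split, on borrowed adult rates and, for the 9 to 11%, on a reading the protocol does not prescribe. The mismatch between objective and analysis depends on none of them.

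The documents do not support saying that the plan will miss real differences because of the chosen analysis. A direct contrast would be underpowered too; what it adds is an honest statement of the uncertainty.

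**What to change.** Keep the within-group intervals. For the secondary objective, do one of two things:

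1. Add, for each pair of groups, the risk difference or ratio in AE proportions with its 95% CI, labelled exploratory. Adjust for gestation at vaccination and basic maternal characteristics where numbers allow. The groups are self-selected, and Appendix 8 admits influenza vaccination at any stage of pregnancy but Tdap only at 30 to 36 weeks, so crude contrasts would be confounded.
2. Reword the objective as a description of AE rates in the three groups, with no comparison claimed.

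In either case, state that 0.081 applies to all 300 Tdap women together, give the widths for plausible group sizes (0.089 to 0.140 for 250 to 100), and say that overlap of group intervals is not evidence of no difference.

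The cost is a few sentences, some extra analysis and a less favourable stated precision. No new data are needed, and the change does not make the comparison well powered.
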